### **6.2 SUMMARIES OF CONDUCT OF STUDY**

The number of subjects who enroll, discontinue, or complete the study will be summarized. Reasons for premature study withdrawal will be listed and summarized. Enrollment and major protocol deviations will be listed and evaluated for their potential effects on the interpretation of study results.

### **6.3 SUMMARIES OF DEMOGRAPHIC AND BASELINE CHARACTERISTICS**

Demographic and baseline characteristics will be summarized using means, standard deviations, medians, and ranges for continuous variables and proportions for categorical variables, as appropriate. Summaries will be presented overall and by treatment.

### **6.4 EFFICACY ANALYSES**

Not applicable.

## 6.5 SAFETY ANALYSES

All subjects who have received at least one dose of balovaptan, whether prematurely withdrawn from the study or not, will be included in the safety analysis.

The safety data, including AEs, laboratory data, and vital signs, will be listed and summarized by treatment. Reasons for withdrawal from study will be listed and summarized. Concomitant medications, 12-lead ECG data, and clinically significant neurological examinations will be listed.

Adverse events will be listed and summarized by treatment, body system and preferred term using the Medical Dictionary for Regulatory Activities. All verbatim AE terms will be mapped to Medical Dictionary for Regulatory Activities (MedDRA) thesaurus terms, and AE severity will be graded according to [Table 2](#).

For laboratory and 12-lead ECG data, subject listings will be presented with abnormalities flagged.

## 6.6 PHARMACOKINETIC ANALYSES

Subjects will be excluded from the PK analysis population if they significantly violate the inclusion or exclusion criteria, deviate significantly from the protocol, or if data are unavailable or incomplete. Excluded cases will be documented together with the reason for exclusion. All decisions on exclusions from the analysis will be made prior to database closure.

Individual plasma concentrations at each sampling timepoint for balovaptan, M2 (as applicable), M3, itraconazole and hydroxy-itraconazole will be presented by listings and descriptive summary statistics by treatment, including means, geometric means, ranges, standard deviations and coefficients of variation. Individual and mean concentration versus time will be plotted on linear and semi-logarithmic scales.

All PK parameters for balovaptan, M2 (as applicable), and M3 will be presented by individual listings and summary statistics by treatment including means, geometric means, medians, ranges, standard deviations and coefficients of variation.

The following balovaptan PK parameters will be estimated:

- $C_{max}$ : Day 10 of Period 1; Day 15 and Day 20 of Period 2
- $AUC_{0-T}$ : Day 10 of Period 1; Day 15 and Day 20 of Period 2
- $T_{max}$ : Day 10 of Period 1; Day 15 and Day 20 of Period 2
- $C_{trough}$ : Day 10 of Period 1; Day 15 and Day 20 of Period 2)
- time to steady state (for balovaptan)

The primary PK parameters are  $C_{max}$  and  $AUC_{0-T}$  for balovaptan, M2, and M3 on Day 10 of Period 1 and Day 20 of Period 2.

A linear mixed model analysis will be applied to analyze the log-transformed primary PK parameters. The model assumes a fixed effect for treatment and a random effect for subject. Estimates of geometric mean ratios together with the corresponding 90% CIs will be derived for the comparisons of the PK parameters as follows:

- balovaptan plus itraconazole (test) vs balovaptan alone (reference)

For itraconazole and hydroxy-itraconazole,  $C_{max}$ ,  $AUC_{0-24h}$ , and  $T_{max}$  will be estimated on Day 5 and Day 20 to evaluate whether adequate levels were reached.

Additional PK parameters may be derived if deemed necessary.

## **6.7 OTHER ANALYSES**

### **6.7.1 Genotyping**

The relationship between CYP3A4 genotype and steady state balovaptan exposure and the influence of CYP3A4 genotype on the effect of itraconazole on balovaptan PK and CYP3A enzyme activity will be evaluated. Other isoforms may also be analysed.

## **6.8 INTERIM ANALYSES**

Interim PK analyses, including the calculation of the PK parameters for both periods, will be done for Cohort A. The data from this analysis will be used in the decision whether the balovaptan dose should be increased from 5 to 10 mg qd for Cohort B.

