#### **1.2.1.1 Clinical Pharmacology**

Exposure of balovaptan increased in a greater than dose-proportional manner following single doses of 0.5 to 76 mg, whereas an approximately linear increase in exposure was observed after repeated dosing with 12 to 52 mg once daily (qd) for 14 days. Balovaptan was rapidly absorbed with a median time to maximum observed plasma concentration ( $T_{max}$ ) between 1 and 4.5 hours after administration of single doses and between 3 and 4 hours following multiple dosing. Steady state was achieved after approximately 7 days; the mean apparent elimination half-life ( $T_{1/2}$ ) after the last dose (Day 14) was approximately 46 hours. Food had no relevant effect on the PK of balovaptan.

In the human mass balance study (Study BP29279), an almost complete absorption of the study drug was observed within the first 72 hours following administration.

The majority of excretion of drug-related material occurred within the first 7 days. Renal excretion was found to be the major pathway of elimination (approximately 53% of the material recovered, mostly composed of metabolites) with the primary route of excretion via metabolism to M1 ( [REDACTED] ) into urine, accounting for approximately 23% of the dose. A further 30% of the administered dose was recovered in feces.

In plasma, steady state exposure to the [REDACTED] metabolite M3 was similar to or slightly higher than that of balovaptan and exposure to the [REDACTED] metabolite M2 was lower than that of parent. M3 and M2 qualify as major metabolites in plasma.

[REDACTED]

There was no clinically/statistically relevant PK interaction with the P-glycoprotein substrate risperidone, one of only 2 approved medications for ASD symptoms in the US, and fluoxetine, a weak CYP3A4 inhibitor often used to treat associated symptoms of ASD. Administration of a single dose of balovaptan 12 mg in combination with itraconazole, a strong CYP3A4 inhibitor, resulted in an increase in the exposure of balovaptan by 1.4-fold for  $C_{max}$  and an approximately 3.1-fold increase for area under the concentration vs time curve from time 0 to 120 hours ( $AUC_{0-120h}$ ). The exposure of metabolite M3 was 1.92- and 1.82-fold lower in terms of  $C_{max}$  and  $AUC_{0-120h}$ , respectively.

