### **1.3 STUDY RATIONALE AND BENEFIT-RISK ASSESSMENT**

The study will be performed in healthy subjects who will not receive any health benefit from participating in this study. The study is necessary for the further development of balovaptan and may be of benefit for future patients.

To date, balovaptan has been investigated in 195 healthy subjects in 5 completed Phase 1 studies (Studies BP25694, BP28318, BP28977, BP29279, and BP29412). One oral relative bioavailability study (Study WP40038) is ongoing (clinically complete, reporting ongoing).

Additionally, balovaptan was investigated in a Phase II study in 148 adult male patients with ASD (BP28420, "VANILLA").

Adverse event (AE) reporting in healthy subjects did not reveal any particular safety alert for balovaptan. The most frequently reported AE was headache, without an apparent dose-response relationship for balovaptan. For the vast majority of AEs, the intensity was rated as mild or moderate. The dose range in these studies was 0.5 to 76 mg (single dose) and 12 to 52 mg (multiple doses for 14 days).

The effect of inhibition of CYP3A4 was previously investigated using a single dose of 12 mg of balovaptan. The study showed that balovaptan  $AUC_{0-120h}$  increased by 3.1-fold and  $C_{max}$  by 1.4-fold in the presence of itraconazole. Mean  $AUC_{0-120h}$  and  $C_{max}$  metabolite M3 were 1.82- and 1.92-fold lower, respectively, in the presence of itraconazole than in the absence of itraconazole. M2 was not measured in that study.

The current study is designed to assess the effect of inhibition of CYP3A4 on the steady state pharmacokinetics of balovaptan after 15 days of coadministration with itraconazole, as balovaptan showed dose and time-dependent PK. Although not reliably measured, analysis of  $AUC_{0-inf}$  in the presence of itraconazole indicated a 4.6-fold increase in balovaptan exposure and plasma  $T_{1/2}$  indicated an increase from 27 to 80 hours. The mean (SD)  $C_{max}$  and  $AUC_{0-T}$  for parent following 14 days of dosing with balovaptan 52 mg qd was 484 (43.1) ng/mL and 5920 (817) h·ng/mL, respectively. M3 was only measured after balovaptan 40 mg for 14 days: the mean (SD)  $C_{max}$  and  $AUC_{0-T}$  were 264 (45.4) ng/mL and 5260 (807) and h·ng/mL, respectively.

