**Figure 1 Study Schema**

Abbreviations: bid = twice daily; PK = pharmacokinetics; qd = once daily

On Period 1 Day 10 and Period 2 Day 20, balovaptan will be dosed at the same time of day. On Period 2 Days 5 and 20 itraconazole will be dosed at the same time of day. On Period 2 Days 6 to 20, itraconazole will be administered in combination with balovaptan.

Subjects will undergo study assessments and procedures, including assessments of AEs and concomitant medications, vital signs, 12-lead ECGs, clinical laboratory evaluations and blood sampling for PK assessments and genotyping as per the schedule of assessments in Appendix 1.

The dose of balovaptan to be used during balovaptan alone and balovaptan plus itraconazole dosing periods will be 5 mg qd for an initial sentinel cohort of 4 subjects (Cohort A). The safety, tolerability, and PK data up to 24 hours after the final dose of balovaptan (when given in conjunction with itraconazole), for at least 3 of the 4 subjects,

will be reviewed by the by the Sponsor's Medical Monitor or designee and the Investigator. There will be at least a 20-day period between Cohort A and Cohort B to allow for analysis of PK data. After review of the data, a dose of balovaptan will be selected for the remainder of subjects (Cohort B). The dose may remain 5 mg qd or may be increased to 10 mg qd, depending on data from Cohort A. The dose may be increased to 10 mg qd for Cohort B if the highest mean exposure values for  $C_{max}$  and  $AUC_{[0-1]}$  in the presence of itraconazole in Cohort A and the projected exposures expected for Cohort B do not exceed the highest exposures seen with multiple dosing of balovaptan 52 mg ( $484 \pm 43.1$  ng/mL for  $C_{max}$  and  $5920 \pm 817$  h-ng/mL for  $AUC_{tau}$ ) and there are no prohibitive safety findings based on a review of safety data from Cohort A. If these criteria are not met, dosing will be continued at 5 mg qd in Cohort B.

If a decision is made to keep the dose at 5 mg qd, a total of 10 subjects will enter Cohort B. If a decision is made to increase the dose to 10 mg qd, a total of 14 subjects will enter Cohort B.

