### **3.3.3 Rationale for Sentinel Group**

As an increase in balovaptan exposure when administered together with itraconazole is expected, to ensure optimal safety of subjects an initial sentinel cohort of 4 subjects (Cohort A) will be enrolled in which the dose of balovaptan will be 5 mg qd. The safety and tolerability and PK data up to 24 hours after the final dose of balovaptan (when

given in conjunction with itraconazole), for at least 3 of the 4 subjects, will be reviewed by the Sponsor's Medical Monitor or designee and the Investigator. After review of the data, a dose of balovaptan will be selected for the remainder of subjects (Cohort B). The balovaptan dose for Cohort B may remain at 5 mg qd or be increased to 10 mg qd. The dose may be increased to 10 mg qd for Cohort B if the highest exposure values for  $C_{max}$  and  $AUC_{[0-\tau]}$  in the presence of itraconazole in Cohort A and the projected exposures expected for Cohort B do not exceed the highest exposures seen with multiple dosing of balovaptan 52 mg (see Section 3.1) and there are no prohibitive safety findings based on a review of safety data from Cohort A by the Sponsor's Medical Monitor or designee and the Investigator.

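### The 10 mg decision rests on an exposure projected from 3 or 4 sentinel subjects, with no stated allowance for sampling error and an inconsistently worded criterion

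*Protocol*

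**What the plan says.** Protocol 6.8 has PK parameters calculated for Cohort A in both periods and states: "The data from this analysis will be used in the decision whether the balovaptan dose should be increased from 5 to 10 mg qd". SAP 7.2 repeats this and refers to a separate interim plan, listed in the SAP references as final on 05-Jul-2018.

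The criterion is in Protocol 3.1 and is repeated in SAP 6.0. It has two exposure tests.

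- **Cohort A:** "The dose may be increased to 10 mg qd for Cohort B if the highest mean exposure values for" Cmax and AUC over the dosing interval, with itraconazole, stay within the 52 mg reference.
- **Cohort B:** "the projected exposures expected for Cohort B do not exceed the highest exposures seen with multiple dosing of balovaptan 52 mg".

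There must also be no prohibitive safety findings. Data "for at least 3 of the 4 subjects" are enough for the review. The reference is printed as 484 ± 43.1 ng/mL for Cmax and 5920 ± 817 h·ng/mL for AUC. Protocol 1.3 and 3.3.2.1 identify these figures as means.

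Protocol 3.3.3 and the synopsis word the Cohort A test differently: "The dose may be increased to 10 mg qd for Cohort B if the highest exposure values for" the same two parameters, without the word mean.

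On the expected size of the interaction, Protocol 1.2.1.1 gives 3.1-fold for AUC0-120h and 1.4-fold for Cmax after a single 12 mg dose. Protocol 1.3 adds that AUC0-inf "indicated a 4.6-fold increase in balovaptan exposure", with the caveat that it was not reliably measured. On dose linearity, Protocol 1.2.1.1 reports that "an approximately linear increase in exposure was observed after repeated dosing with 12 to 52 mg once daily", while single doses from 0.5 to 76 mg were more than dose proportional.

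**The concern.** The sentinel step is there to protect healthy volunteers from exposures beyond those already studied. Cohort A is dosed at 5 mg, so its own exposure should lie well below the 52 mg reference, and the test that matters is the projection to 10 mg. That projection comes from 3 or 4 people and is applied to 14 new ones.

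The protocol quantifies precision for 12 completers in the final analysis, but neither document does so for the sentinel projection. If the projection is read as a single value, it can fall below the reference while the true average at 10 mg lies above it, and the printed rule would not show how likely that is.

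The wording adds a second problem. A comparison of means, a comparison of highest individual values, and a mixture of the two are different rules, and the sections do not agree on which applies.

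**Working it through.** **1. The plan's own precision figure.** Protocol 6.1 gives a 90% CI factor of 1.30 for 12 subjects at CV 39%. With s = sqrt(ln(1 + 0.39²)) = 0.376, the factor is exp(t × s × sqrt(2/12)). This is 1.302 with t on 22 df and 1.318 with the paired 11 df. The figure reproduces.

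**2. The Cohort A test.** By linear scaling from 52 mg, AUC at 5 mg with itraconazole is 5920 × 5/52 × 4.6 = 2618 h·ng/mL. That is 44% of 5920, so on these figures this test hardly binds.

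**3. The projection to 10 mg.** AUC at 10 mg alone is 5920 × 10/52 = 1138. Multiplying by the interaction ratio gives:

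| Ratio assumed | Projected AUC | Share of 5920 | 5920 / projection |
|---|---|---|---|
| 3.1 (AUC0-120h) | 3529 | 60% | 1.68 |
| 4.6 at 95.6% of steady state | 5005 | 85% | 1.18 |
| 4.6 (AUC0-inf) | 5237 | 88% | 1.13 |

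The 95.6% is 1 − 2^(−360/80), for 15 daily doses and a half-life of 80 h.

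The two ratios are compatible. Under one-compartment decay with half-lives of 27 and 80 h, 3.1-fold over 120 h implies 3.1 × 0.954/0.646 = 4.58-fold to infinity. This is a consistency check and not independent confirmation, because the 80 h half-life comes from the same single-dose comparison.

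**4. Cmax.** The single-dose ratio gives 484 × 10/52 × 1.4 = 130 ng/mL, 27% of 484. Accumulation with the longer half-life would reduce that room. If Cmax also rose 4.6-fold, it would be 428 ng/mL, or 88%.

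**5. Sampling error of the sentinel mean.** The 90% CI factor of a geometric mean is exp(t(0.95, n−1) × s/√n). The documents give no between-subject CV with itraconazole, so two values are used as a range: 13.8% (817/5920, the 52 mg spread; s = 0.137) and 39% (labelled within-subject in Protocol 6.1, taken here as total CV; s = 0.376).

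| CV | n | One SE, as a factor | 90% CI factor |
|---|---|---|---|
| 13.8% | 4 | 1.07 | 1.18 |
| 13.8% | 3 | 1.08 | 1.26 |
| 39% | 4 | 1.21 | 1.56 |
| 39% | 3 | 1.24 | 1.89 |

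**6. Comparison with the margin.** At 4.6-fold (margin 1.13), all four 90% factors exceed the margin, while one SE exceeds it only at CV 39%. At 3.1-fold (margin 1.68), only the n = 3, CV 39% factor exceeds it.

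**7. Chance of a misleading pass.** Suppose the true geometric mean at 10 mg were 1.13 times the reference. A point projection would fall at or below the reference with probability Φ(−ln 1.13 / (s/√n)). This is 26% (n = 4) or 29% (n = 3) at CV 39%, and 4% or 6% at CV 13.8%.

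**8. Effect of how the reference is read.** The highest individual 52 mg value is not given. If mean + 1 SD (5920 + 817 = 6737) stands in for a higher reference, the margin at 4.6-fold is 6737/5237 = 1.29. This is above the 90% factors at CV 13.8% and below those at CV 39%.

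**The case against.** The strongest reply has five parts.

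- **The narrow margin is one end of a range.** It needs the 4.6-fold ratio that the protocol itself qualifies, and it concerns AUC only. A reader might infer that the projection is known to lie within 13% of the limit and that this is less than its sampling error. The documents do not support that. The range is 1.13 to 1.68, and at CV 13.8% one standard error is 7% to 8%, which is smaller than 13%. This stands.
- **Individuals above 5920.** A reader might also count how many of the 14 new subjects would exceed 5920 and call those exposures unprecedented. But 5920 is a mean. If the 52 mg distribution was roughly symmetric, about half of those subjects were already above it. This stands, and no such count is used here.
- **The projection method is not stated to be a point estimate or a simple doubling.** Protocol 3.3.2.1 cites population modelling at 10 mg, and the separate interim plan may hold a method and a margin. This stands as a limit: the gap can be asserted only for the protocol and SAP.
- **Non-linearity cuts both ways.** More-than-proportional exposure would make doubling from 5 mg too low, but it would also make linear scaling down from 52 mg too high and the true margin wider. This stands, and is why both scalings should be shown.
- **The rule is permissive and has a safety condition.** An increase is allowed and never required, and review by the Medical Monitor and the Investigator is built in. True, but that review is not a statement of how uncertain the projection is.

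None of this supplies the missing allowance or removes the disagreement between sections.

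**Conclusion.** The point holds in a limited form. The protocol and SAP let a projection from as few as 3 subjects inform the 10 mg decision and state no allowance for sampling error. On the protocol's figures the 52 mg mean AUC is 1.68 to as little as 1.13 times the projection, and at the narrow end that margin is smaller than the 90% interval of a 3- or 4-subject mean under either CV. For Cmax the single-dose ratio leaves wide room, less after accumulation.

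These sizes assume linear scaling from 52 to 10 mg (below the 12 to 52 mg range where linearity was seen), single-dose interaction ratios applied at steady state, a total CV between 13.8% and 39%, and 5920 as the reference.

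Separately, and without any assumption, the criterion is inconsistent: highest mean values in Protocol 3.1 and SAP 6.0, highest values in Protocol 3.3.3 and the synopsis, and a reference described as the highest exposures seen but printed as mean ± SD. Until these are reconciled the margin is not defined.

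**What to change.** 1. Reconcile the synopsis, Protocol 3.1, 3.3.3 and 6.8, and SAP 6.0 and 7.2, on two matters: whether average or individual exposures are compared, and whether the 52 mg reference is the mean or the highest observed value.
2. In Protocol 6.8, SAP 7.2 and the interim plan, state how the projection is made. Report the projected geometric mean Cmax and AUC0-tau at 10 mg, from Cohort A on Period 2 Day 20, each with a 90% CI and a prediction limit for a single new subject. Show them under the stated scaling assumption and under a more-than-proportional one, against the reconciled reference. If the interim plan already does this, a cross-reference is enough.

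The cost is one table from data already in the interim analysis, plus wording. The downside is that with 3 or 4 subjects the intervals will be wide and the projection will look less favourable than a single value. The choice of limit and the dose decision remain the sponsor's.

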## **7. DATA COLLECTION AND MANAGEMENT**

### **7.1 DATA QUALITY ASSURANCE**

The Sponsor will supply eCRF specifications for this study. The contract research organization (CRO), PRA Health Sciences (PRA), will be responsible for data management of this study, including quality checking of the data. Data entered manually will be collected via EDC through use of eCRFs. Sites will be responsible for data entry into the EDC system. In the event of discrepant data, PRA will request data clarification from the sites, which the sites will resolve electronically in the EDC system.

PRA will produce a Data Quality Plan that describes the quality checking to be performed on the data. Central laboratory data will be sent directly to PRA using PRA's standard procedures to handle and process the electronic transfer of these data.

The Sponsor will perform oversight of the data management of this study, including approval of the PRA's data management plans and specifications. Data will be periodically transferred electronically from PRA to the Sponsor, and the Sponsor's standard procedures will be used to handle and process the electronic transfer of these data.

Electronic case report forms and correction documentation will be maintained in the EDC system's audit trail. System backups for data stored at the CRO and records retention for the study data will be consistent with the CRO's standard procedures.

## **7.2 ELECTRONIC CASE REPORT FORMS**

Electronic case report forms are to be completed through use of a Sponsor-designated EDC system. Sites will receive training and have access to a manual for appropriate eCRF completion. eCRFs will be submitted electronically to the Sponsor and should be handled in accordance with instructions from the Sponsor.

All eCRFs should be completed by designated, trained site staff. Electronic case report forms should be reviewed and electronically signed and dated by the Investigator or a designee.

At the end of the study, the Investigator will receive subject data for his or her site in a readable format on a compact disc that must be kept with the study records.

Acknowledgement of receipt of the compact disc is required.

## **7.3 ELECTRONIC PATIENT-REPORTED OUTCOME**

Not applicable.

## **7.4 SOURCE DATA DOCUMENTATION**

Study monitors will perform ongoing source data verification and review to confirm that critical protocol data (ie, source data) entered into the eCRFs by authorized site personnel are accurate, complete, and verifiable from source documents.

Source documents (paper or electronic) are those in which subject data are recorded and documented for the first time. They include, but are not limited to, hospital records, clinical and office charts, laboratory notes, memoranda, patient-reported outcomes, evaluation checklists, pharmacy dispensing records, recorded data from automated instruments, copies of transcriptions that are certified after verification as being accurate and complete, microfiche, photographic negatives, microfilm or magnetic media, X-rays, patient files, and records kept at pharmacies, laboratories, and medico-technical departments involved in a clinical trial.

Before study initiation, the types of source documents that are to be generated will be clearly defined in the Trial Monitoring Plan. This includes any protocol data to be entered directly into the eCRFs (ie, no prior written or electronic record of the data) and considered source data.

Source documents that are required to verify the validity and completeness of data entered into the eCRFs must not be obliterated or destroyed and must be retained per the policy for retention of records described in Section [7.6](#).

To facilitate source data verification and review, the investigators and institutions must provide the Sponsor direct access to applicable source documents and reports for trial-related monitoring, Sponsor audits, and IRB/EC review. The study site must also allow inspection by applicable health authorities.

